## **6. Training**

All 20 clinics will receive hands-on, in-person intervention training for their staff, conducted by a physician investigator, a project manager or coordinator, and the clinic's Care Delivery Supervisor. Training will be conducted in June and July of 2017, prior to the official start of the study interventions.

All clinics will receive training on:

- The hypertension management workflow, including best practice alerts and referral orders for hypertension care
- Communication with patients about hypertension care referrals
- Follow-up with patients regarding unscheduled or missed referral visits
- Omron BP machine best-practice use, re-emphasize need for second BP when elevated

Telehealth clinics will receive training on:

- Details of telemonitoring program for discussion with patients
- Operation of telemonitoring equipment and technical support options
- Use of patient-entered vitals flowsheet (in EMR)

We will include all primary care team members in these initial trainings, including PCPs, RNs, MA/LPNs, and MTMs. We will keep a roster of all staff in these positions at each clinic, and monitor attendance at trainings. The best training format will be determined by the clinic Care Delivery Supervisor. We will record a webinar presentation of our basic training to supplement the in-person/hands-on training, for review by staff who couldn't attend or for use as a reference. After each in-person training we will collect evaluation feedback to determine whether the training is meeting the needs of each clinic.

Care Delivery Supervisors will be provided with a simple 1-2 page “guide” for the hypertension care interventions, so they may continue to support their staff in reinforcing best practices.

Need for follow-up trainings will be determined at the conclusion of the initial in-person training.

The following training materials will be developed by the study team with input from stakeholders by May 2017:

1. Detailed outline of training objectives
2. Scripts for patient communication about interventions (central outreach, nursing, physicians, pharmacists)
3. After Visit Summary content with patient instructions
4. Frequently Asked Questions for both interventions
5. Guide for Care Delivery Supervisors
6. Instructions for set-up and use of Telemonitoring Equipment (Telehealth Clinics only)

Further training will be provided during in-person visits from the study staff to clinics throughout the intervention period. At least 10 clinics will receive a quarterly in-person visit by a study coordinator and all clinics receive in-person visits for continued training and evaluation every six months. The content and objectives of these in-person visits is to be determined.

## **7. Outcomes**

The study outcomes have been selected based on input directly elicited from patients and other stakeholders participating in this project. The Aim 1 outcomes address the relative effectiveness of clinic-based care and telehealth care in improving key clinical and patient-reported outcomes (Table 1). The Aim 2 outcomes are directed toward evaluating intervention implementation fidelity (Table 2) and other RE-AIM measures (Table 3). No additional research visits will take place to gather outcomes data.

### **7.A. Primary Aim 1 outcome**

The primary outcome is change in SBP after 12 months of follow-up (H1.1). SBP values that are routinely collected in primary care will be extracted from the vital signs field in the EHR at the two qualifying encounters and at all subsequent qualifying encounters over the next 24 months for all enrolled patients.

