## **10. Analysis**

## 10.A Aim 1 Primary and Secondary Analyses

The Aim 1 hypotheses pertain to the effectiveness of telehealth care, predicting that, relative to clinic-based care, it will improve SBP by a practically meaningful 5 mm Hg after 12 months of follow up (H1.1) and patient-reported outcomes (PRO) after 6 months of follow up (H1.2). H1.1 will be tested using random coefficients models in which post-enrollment SBP values will be predicted from clinic-randomized treatment group (Telehealth), time elapsed from enrollment to the SBP (YEARS), and the treatment by time interaction. The most basic form of the H1.1 model will be:

$$SBP_{ij} = \gamma_{00} + \gamma_{10} \text{Telehealth}_i + \gamma_{01} \text{YEARS}_j + \gamma_{11} \text{Telehealth}_i * \text{YEARS}_j + [u_{i0} + e_{ij}],$$

where EHR-derived SBP values documented at all qualifying encounters for 24 months will vary randomly across randomized clinics ( $u_{i0}$ ) and time ( $e_{ij}$ ). Enrolled patients will be assigned to the treatment group to which their clinic is randomly assigned, regardless of their adherence to any component of the clinic-based care or telehealth care approaches. YEARS will be scaled so that 0 represents the date of the primary care encounter at which the patient was enrolled in the study and 1 represents 365 days later. Parameter  $\gamma_{01}$  will therefore estimate the annual rate of change in SBP among clinic-based care patients, and parameter  $\gamma_{11}$  will estimate the difference in rate of SBP change among telehealth relative to clinic-based care patients. The H1.1 model will be adapted for H1.2 by replacing the YEARS component of  $\gamma_{01}$  and  $\gamma_{11}$  with a dummy indicator (6M) for whether the PRO is an enrollment or 6-month survey response.

SBP and PRO are expected to be approximately normally distributed, although the suitability of alternate error distributions and link functions will be assessed if their distributions depart from expectations. Should we observe an imbalance between study groups in the characteristics of randomized clinics, particularly in factors that moderate the fidelity with which the care models may be implemented, we may include clinic-level variables (e.g., % patients >65) as covariates or treatment modifiers, as appropriate.

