### 10.A.1. Aim 1 Other Analyses

We plan to explore whether treatment effects differ among patient groups defined by age, race/ethnicity, socioeconomic status, and comorbidity. While we anticipate that on average across all patient groups telehealth care will reduce SBP by 5 mm Hg more than clinic-based care, we will separately quantify the treatment effect for all H1 outcomes among targeted patient subgroups. The H1 analytic models can be easily adapted to include parameters for patient covariates as well as interactions of patient covariates with time or time by treatment.

[figure not shown]
The H1 analytic models can be readily adapted for secondary and sensitivity analyses. As presented, H1.1 assumes a linear rate of change in SBP over time. The model can be readily adapted to assess the immediate effectiveness of telehealth during the first 6 months following eligibility separately from the 6- to 12- and 12- to 24-month periods, when short-term improvements in SBP or PROs may be differentially maintained over a longer time frame. Similarly, parameters  $\gamma_{01}$  and  $\gamma_{11}$  can be allowed to vary randomly so that the rate of SBP change is different for each of the 20 randomized clinics. We could then assess, for example, whether clinic-specific rates of change are related to clinic characteristics or the fidelity with which the care model was implemented.

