### 4. Patient outcomes and safety monitoring

4.1 Effectiveness, clinical outcomes. The primary clinical effectiveness analyses will quantify the extent to which there is a larger reduction, or less of an increase, in systolic blood pressure in the 12 months following Hyperlink enrollment among patients in telehealth relative to clinic-based care clinics. Secondary analyses will address whether similar changes are observed in clinical outcomes such as diastolic blood pressure, lipid levels and cardiovascular risk; whether antihypertensive or lipid medications are more aggressively managed among telehealth patients; and whether telehealth patients are less likely to be current smokers. Table 1 summarizes all primary and secondary outcomes. For each clinical outcome, we plan to include all available data in the 24 months following enrollment in the analyses. However, effectiveness will be assessed via a comparison of the rate of change in the first 12 months post-enrollment.

All clinical outcomes data will be documented in the electronic health record or the Hyperlink data repository as observations accrue. Their immediate availability will make it feasible to check assumptions of the clinical effectiveness analyses such as balance on key covariates prior to intervention exposure; the central tendency, variance and distribution of clinical outcomes; the number and timing of observations per person; the viability of assuming a linear rate of change in outcomes, and how non-linear trends might be addressed; and the magnitude of the design effects introduced by cluster randomization and repeated measures within patients. These assumptions can be investigated in aggregate as data accrue, and by treatment group or clinic at the DSMB's request, to inform the conduct of the primary effectiveness analyses.

4.2 Effectiveness, patient outcomes. The effectiveness of the clinic-based care and telehealth care interventions at improving patient reports of side effects, satisfaction with care and confidence in self-care will be assessed by comparing

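### Sections 7.A and 10.A do not settle whether the enrollment-encounter SBP enters the H1.1 model, and under an early-plateau effect that choice moves the tested slope by roughly 0.5 to 3 mm Hg

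*Combined protocol and SAP*

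**What the plan says.** Section 7.A makes change in SBP after 12 months the primary outcome. It says SBP will be extracted from the EHR "at the two qualifying encounters and at all subsequent qualifying encounters over the next 24 months for all enrolled patients". The second qualifying encounter is the one at which the patient is enrolled (sections 4.C and 4.D).

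Section 10.A says: "H1.1 will be tested using random coefficients models in which post-enrollment SBP values will be predicted from clinic-randomized treatment group". The other predictors are elapsed time and the treatment-by-time interaction. The basic equation has no baseline SBP term. On the time scale: "YEARS will be scaled so that 0 represents the date of the primary care encounter at which the patient was enrolled in the study". A later clause in the same section says that SBP from all qualifying encounters for 24 months enters the model. The effect parameter, γ11, "will estimate the difference in rate of SBP change among telehealth relative to clinic-based care patients". H1.1 is most strongly supported if γ11 is -5.0 or lower with P < .05. The arm difference at time 0, γ10, is not tested.

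Section 10.A.1 adds: "As presented, H1.1 assumes a linear rate of change in SBP over time". The monitoring plan (section 15, item 4.1) says that "effectiveness will be assessed via a comparison of the rate of change in the first 12 months post-enrollment", and its Table 4 lists a trend from enrollment to 12 months.

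No section states the role of the enrollment SBP in H1.1.

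**The concern.** A change needs a starting value. If 10.A is followed literally, the first modelled SBP is the first one after enrollment, and γ11 measures only what happens among follow-up readings. Any separation of the arms that has occurred by then goes largely into γ10.

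The protocol gives reason to expect early separation. Section 5.B (third modification) reports from the earlier trial that BP lowering was greatest after about 3 months on average, with little added later. A sustained benefit of that shape appears in a follow-up-only model mostly as an intercept difference, which the hypothesis test does not examine. With the enrollment SBP included at YEARS = 0, much of the same benefit moves into the slope.

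Two analysts could therefore follow the same plan on the same data, report clearly different primary estimates, and in some settings fall on opposite sides of the -5.0 mark.

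**Working it through.** **1. The plan's own figure.** Section 10.A.3 gives detectable standardized effects of .124 (clinic ICC .01) and .174 (ICC .03). It assumes 20 clinics of 100 patients, 3 SBPs each over 24 months, 80% power and α = .05. The formula is not stated. This one reproduces the figures:

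MDSE = (1.960 + 0.842) × √[2(1 − ICC)(1 + 99·ICC) / (1000·Sxx)], with Sxx = 2 (SBPs at 0, 1 and 2 years).

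- ICC .01: 2.802 × √(2 × 0.99 × 1.99 / 2000) = 0.124
- ICC .03: 2.802 × √(2 × 0.97 × 3.97 / 2000) = 0.174

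Multiplied by the SD of 20.4, these are 2.53 and 3.55 mm Hg, as stated. The spacing that fits has one SBP at time 0. That hints that planning counted an enrollment value, but it is my inference.

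**2. Inputs for the contrast.**

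- From the documents: the 5 mm Hg effect (H1.1), the peak at about 3 months (5.B), 3 SBPs per patient (10.A.3), and 12- and 24-month windows (section 15, item 4.1, and 10.A).
- Assumed: the effect builds linearly to 3 months and then stays flat; all 3 SBPs are follow-up readings, at times uniform over the window; visit timing and mean enrollment SBP are alike in both arms.

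The arm difference at time t in years is d(t) = −5·min(t/0.25, 1). The model has a clinic intercept only, so the expected coefficients are γ11 = Cov(t, d)/Var(t) and γ10 = E[d] − γ11·E[t], taken over the modelled records.

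**3. Twelve months, follow-up only.**

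- E[t] = 0.5; Var(t) = 1/12
- E[d] = −5(1 − 0.125) = −4.375
- E[td] = −5[0.25²/3 + (1 − 0.25²)/2] = −2.448
- Cov = −2.448 + 0.5 × 4.375 = −0.260
- γ11 = −0.260 × 12 = **−3.1**; γ10 = −2.8

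**4. Twelve months, enrollment SBP added.** One record in four now has t = 0 and d = 0, so each raw moment is multiplied by 3/4.

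- E[t] = 0.375; Var(t) = 0.25 − 0.375² = 0.1094
- E[d] = −3.281; E[td] = −1.836
- Cov = −1.836 + 0.375 × 3.281 = −0.6055
- γ11 = −0.6055/0.1094 = **−5.5**; γ10 = −1.2

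**5. Twenty-four months, same steps.**

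- Follow-up only: E[t] = 1, Var(t) = 1/3, E[d] = −4.6875, E[td] = −4.974, Cov = −0.2865. γ11 = **−0.9**; γ10 = −3.8.
- Enrollment SBP added: E[t] = 0.75, Var(t) = 0.4375, E[d] = −3.516, E[td] = −3.730, Cov = −1.094. γ11 = **−2.5**; γ10 = −1.6.

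| Window | γ11 without | γ11 with | Shift |
|---|---|---|---|
| 12 months | −3.1 | −5.5 | 2.4 |
| 24 months | −0.9 | −2.5 | 1.6 |

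**6. Other assumptions.** I varied the 3-month plateau over 2 to 8 follow-up SBPs, uniform or early-weighted visits, and within-patient correlation 0 or .28. The shift runs from roughly 0.5 to 3 mm Hg. The largest value, 3.1, needs a 12-month window, 2 follow-up SBPs and correlation .28. More readings, or readings bunched soon after enrollment, shrink it. With an exactly linear effect, d(t) = −5t, both record sets give γ11 = −5.0 and the shift is zero.

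**The case against.** The best defence is that this is a wording gap on top of a disclosed linearity assumption. If the effect is linear, including the enrollment SBP changes nothing. Section 10.A.1 states the assumption and offers period-specific models, and section 15 (item 4.1) plans to check it. YEARS = 0 at enrollment and the trend described as running from enrollment both suggest that the enrollment value was meant to be included. All of that is fair. It does not settle the question, because 10.A's opening description says otherwise and the basic model has no other place for a baseline. The protocol's own earlier data also point away from a straight line.

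A second objection is that the enrollment SBP could be a covariate. That would be legitimate, but a covariate with similar means in both arms does not anchor the slope at time 0, so γ11 would stay near the follow-up-only value.

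Third, the enrollment SBP was selected for being high, and section 10.A.2 warns that enrollment may differ by arm. Regression to the mean cancels in γ11 only if selection and visit timing are alike in both arms. This stands as a limit on the fix.

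A reader might go further and infer that 7.A builds the outcome from both qualifying SBPs, so that untreated time before enrollment enters the slope and biases it even when the effect is linear. The documents do not support that. Section 7.A says these values are extracted, they are also needed for eligibility, and no modelling text places a record before YEARS = 0.

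**Conclusion.** The concern holds for the enrollment-encounter SBP. Sections 7.A and 10.A leave its role open, and the choice changes what γ11 measures. Under a 5 mm Hg effect reached by 3 months and sustained, with three uniformly timed follow-up readings, γ11 moves from about -3.1 to -5.5 over 12 months and from about -0.9 to -2.5 over 24 months. In that 12-month setting, whether the -5.0 mark is met turns on this choice alone; over 24 months neither version reaches it.

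The size depends on assumed shape and visit timing. The range of roughly 0.5 to 3 mm Hg is not a bound, and the shift is zero under a linear effect. Nor should it be said to exceed the detectable effect of 2.53 to 3.55 mm Hg. That figure assumes 24 months of data, where the base-case shift is 1.6.

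The point should be resolved before analysis, but it does not invalidate the design.

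**What to change.** - In 10.A, replace the restriction to values after enrollment with an explicit record set: the enrollment-encounter SBP as the YEARS = 0 record, plus all later qualifying SBPs in the window. H1.2 already treats the enrollment survey response as an outcome record, so the two models would then agree.
- In 7.A, state that the prior qualifying SBP is extracted for eligibility and description only and is not an outcome record.
- In 10.A.3, say whether the three SBPs per patient include the enrollment value.

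The cost is wording only, since all the values are already extracted. The change ties γ11 to change from enrollment but does not make a straight line fit a plateau: with the enrollment SBP included, a sustained 5 mm Hg effect still gives -5.5 over 12 months and -2.5 over 24. The shape of the time trend has to be dealt with separately.

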### **7.B. Secondary Aim 1 outcomes**

Aim 1 patient-reported secondary outcome measures are treatment side effects; experiences and satisfaction with hypertension care; home BP self-monitoring; and confidence in self-care. These outcome data will be collected using patient surveys. These patient-reported secondary outcome measures were selected based on 1) patient ratings of importance, 2) evidence that previous similar telehealth interventions led to improvements, 3) importance of the measure as a potential mediator of intervention effect, and 4) the measure cannot be obtained from the EHR, claims or any other routinely collected patient data. All enrolled patients will be mailed a baseline survey that includes primary patient-reported outcome measures within one week of their qualifying encounter, with telephone follow-up of non-responders. They will also be asked to complete follow-up surveys 6, 12 and 24 months later that will be administered by mail, telephone or electronically according to the patient’s preference. The secondary Aim 1 analyses will focus on patient reports in the baseline and 6 month surveys. A draft of the patient survey is included in Appendix H.

Patients’ reports of BP treatment-related side effects will be assessed using the Treatment Satisfaction Questionnaire for Medication (TSQM) and a side effect symptom checklist modeled after the PERSYVE questionnaire. The TSQM global satisfaction and effectiveness, side effects, and convenience subscales demonstrate adequate internal consistency

(Cronbach  $\alpha$  = .86-.90) and positive correlation with self-reported health. Among patients with hypertension, all three subscales were correlated with global medication satisfaction.

Patient Assessment of Chronic Illness Care (PACIC). The PACIC will quantify patient experience of hypertension care, including self-management support, along dimensions in the Chronic Care Model. The overall PACIC scale has demonstrated excellent internal consistency (Cronbach  $\alpha$  = .93; subscale  $\alpha$  = .77-.90) and adequate test-retest reliability over 3 months (overall .58; subscales .47-.68). It has been shown to be highly responsive to a telehealth intervention for hypertension.

Satisfaction with health care provider communication will be measured with the 6 items from the Clinic & Group Consumer Assessment of Healthcare Providers and Systems (CG-CAHPS). The CG-CAHPS survey is a product of the Agency for Healthcare Research and Quality's CAHPS program, which is a public-private initiative to develop and maintain standardized surveys of patients' experiences with ambulatory and facility-level care. The scale has good internal consistency (Cronbach  $\alpha$  = .89), is highly correlated with overall physician ratings, and the scale items have been shown to be responsive to a previous telehealth care intervention. In addition, this subset of items is currently in use to assess patient satisfaction with care at HealthPartners clinics and other medical groups nationally as part of the NRC Picker 'Connect Experience' survey. BP self-monitoring rates and confidence in self-care will be measured by items used in previous research that have been shown to be responsive to intervention.

### **7.C. Aim 1 other outcomes**

Other clinical outcomes include cardiovascular risk factors other than systolic BP (DBP, lipid levels, statin use, antihypertensive medication use, smoking, and overall cardiovascular risk based on 10-year AHA/ACC pooled risk equations and the Framingham 30-year risk equation that may be influenced directly or indirectly by telehealth care relative to clinic-based care. The study will also monitor laboratory abnormalities in electrolytes and kidney function that may be affected by hypertension medications, as well as low blood pressure (hypotension) and fainting that might result from overly aggressive blood pressure lowering. All secondary clinical outcome values and dates are routinely documented in the EHR as they are measured at clinic encounters or are returned as laboratory values.

The patient survey will also include some items and scales that do not meet the criteria for secondary outcomes but have been identified by patients or investigators as potentially important, as well as all responses from the 12 and 24 month surveys.

### **7.D. Aim 2 outcomes**

The Aim 2 analyses are directed toward evaluating intervention uptake and providing timely feedback to clinic and care teams to improve fidelity to both interventions. We will rely on two well-accepted frameworks, the RE-AIM framework and the Consolidated Framework for Implementation Research (CFIR) to identify barriers and facilitators to adoption, implementation, and maintenance; monitor intervention implementation progress and adaptations; and interpret reasons for variations in implementation success or failure. The reach, adoption, implementation and maintenance of both interventions will be evaluated using the definitions of each measure found in Tables 2 and 3.

## **8. Measurements**

### **8.A. EHR for clinical measures**

The primary outcome, SBP, and other clinical outcomes will be extracted from data documented in the electronic health record (EHR). An EHR tool that operates in HealthPartners primary care clinics is automatically triggered when vital sign

data are saved to the EHR. The tool searches the EHR to gather the most recent vital signs (e.g., SBP, DBP) and laboratory values (e.g., total cholesterol, LDL, potassium, sodium, creatinine), current medications (e.g., antihypertensive medications, statins), lifestyle data (e.g., smoking status, BMI), safety events (hypotension, fainting), and socio-demographic information (e.g., age, ethnicity, race). These data elements are used to calculate total cardiovascular risk (e.g., 10 year Hard CV risk via the ACC/AHA risk model; 30 year lifetime risk via the Framingham model) and to alert the provider to abnormalities (e.g., potassium, sodium, creatinine values that are out of range). The EHR tool documents the information that was aggregated for each triggering event, including the dates that were associated with each data element (e.g., date of cholesterol test). The tool also assigns a random unique identifier to each patient so that data elements stored in the EHR as part of routine care may be readily extracted and re-assembled to describe within-person changes in clinical outcomes over time.

